9.1.2 Serious Adverse Event

An SAE is any AE occurring at any dose that results in any of the following outcomes: death, a life-threatening AE, inpatient hospitalization or prolongation of existing hospitalization, a persistent or significant disability/incapacity, or a congenital anomaly/birth defect. Important medical events that may not result in death, be life-threatening, or require hospitalization may be considered an SAE when, based upon appropriate medical judgment, they may jeopardize the patient, or the patient may require medical or surgical intervention to prevent one of the outcomes listed in this definition. See Section 9.3 for procedures for reporting an SAE.

Allergan considers all cancer AEs as SAEs. In addition, Allergan considers any abortion (spontaneous or nonspontaneous) as an SAE.

Preplanned surgeries or procedures for pre-existing, known medical conditions for which a patient requires hospitalization are not reportable as SAEs.

Any preplanned surgery or procedure should be clearly documented in the site source documents by the medically qualified investigator at the time of the patient’s entry into the study. If it has not been documented at the time of the patient’s entry into the study, then it should be documented as an SAE and reported to Allergan.

9.1.3 Severity

A clinical determination will be made of the intensity of an AE. The severity assessment for a clinical AE must be completed using the following definitions as guidelines:

Mild	Awareness of sign or symptom, but easily tolerated
Moderate	Discomfort enough to cause interference with usual activity
Severe	Incapacitating with inability to work or do usual activity

9.1.4 Relationship to Study Drug or Study Procedure

A determination will be made of the relationship (if any) between an AE and the study drug or study procedure, as applicable. A causal relationship is present if a determination is made that there is a reasonable possibility that the AE may have been caused by the drug or study procedure.

9.2 Procedures for Reporting Adverse Events

Any AE must be recorded on the appropriate eCRF.

All SAEs that are drug-related and unexpected (not listed as treatment-related in the current Investigator's Brochure) must be reported to the governing Institutional Review Board/Independent Ethics Committee (IRB/IEC) as required by the IRB/IEC, local regulations, and the governing health authorities. Any AE that is marked “ongoing” at the exit visit must be followed-up as appropriate.

9.3 Procedures for Reporting a Serious Adverse Event

Any SAE occurring during the study period (beginning with informed consent) and for at least 30 days after the last dose of study drug must be immediately reported no later than 24 hours after learning of an SAE. SAEs must be reported to Allergan or Agent of Allergan (eg, contract research organization [CRO]) and recorded on the SAE form. All patients with an SAE must be followed up and the outcomes reported. The investigator must supply Allergan and the IRB/IEC with any additional requested information (eg, autopsy reports and discharge summaries).

In the event of an SAE, the investigator must:

1. Notify Allergan immediately by fax or email using the SAE form (contact details can be found on page 1 of the SAE form); the fax number is on the front page of this protocol, and phone numbers and relevant Allergan personnel contacts are also on the study contacts page.
2. Obtain and maintain in his/her files all pertinent medical records, information, and medical judgments from colleagues who assisted in the treatment and follow-up of the patient.
3. Provide Allergan with a complete, written description of the AE(s) on the SAE form describing the event chronologically, including any treatment given (eg, medications administered, procedures performed) for the AE(s). Summarize relevant clinical information about the event: signs, symptoms, diagnosis, clinical course and relevant

clinical laboratory tests, etc. Include any additional or alternative explanation(s) for the causality which includes a statement as to whether the event was or was not related to the use of the investigational drug.

4. Promptly inform the governing IRB/IEC of the SAE as required by the IRB/IEC, local regulations, and the governing health authorities.

9.4 Exposure to Investigational Product During Pregnancy

Study center personnel must report every pregnancy (from the time the patient signs the ICF for the trial until 30 days after the last dose of ubrogepant), on the Pregnancy Form as soon as possible (within 24 hours of learning of the pregnancy) to the SAE/pregnancy fax number, [REDACTED] even if no AE has occurred. Pregnancies in female partners of male patients must also be reported. The pregnancy must be followed to term, and the outcome reported by completing a follow-up Pregnancy Form. If, however, the pregnancy is associated with an SAE (eg, if the mother is hospitalized for hemorrhage), in addition to the Pregnancy Form, a separate SAE Form must be filed as described in Section 9.3 with the appropriate serious criterion (eg, hospitalization) indicated.

9.5 ALT or AST Elevations

A post-treatment event of ALT or AST ≥ 3 times the ULN is considered an Event of Clinical Interest. Any patient with this laboratory result after ubrogepant was taken should have repeat testing within 48 to 72 hours to confirm the abnormality. For this repeat testing, the following tests should be performed: hematology and chemistry panels, international normalized ratio (INR), and a toxicology screen for acetaminophen. In addition, the investigator should perform a complete history and examination to evaluate for possible liver disease.

All ALT or AST elevations ≥ 3 times the ULN must be reported to Allergan using the AE of Interest Form and submitted within 24 hours of the time the investigator becomes aware of the event. All new elements of history, physical examination, diagnostic testing results, and other relevant medical reports are to be reported for each event.

If an ALT or AST elevation ≥ 3 times the ULN is confirmed and the patient meets any of the following criteria, close medical follow-up is required:

- Patients with ALT or AST ≥ 3 times ULN and ≤ 5 times the ULN and who are asymptomatic with regard to possible liver disease (ie, no fatigue, nausea, vomiting, right upper quadrant pain or tenderness, fever, rash, or eosinophilia [$> 5\%$])

- Patients with ALT or AST ≥ 3 times ULN and ≤ 5 times the ULN and (total bilirubin < 2 times the ULN and INR < 1.5)

Patients who meet these criteria should be followed clinically, and further medical evaluation should be performed per the judgment of the investigator and in conjunction with medical personnel at Allergan. The chemistry panel should be repeated 1 to 2 times per week to follow the course of ALT/AST elevation. An extra blood sample should be collected and sent to the central laboratory for further diagnostic testing at a later date if needed.

If an ALT or AST elevation ≥ 3 times the ULN is confirmed and the patient meets any of the following criteria, close medical follow-up is required:

- ALT or AST ≥ 3 times the ULN and the patient is symptomatic with the appearance of fatigue, nausea, vomiting, right upper quadrant pain or tenderness, fever, rash, or eosinophilia ($> 5\%$)
- ALT or AST ≥ 3 times the ULN **and** total bilirubin > 2 times the ULN or INR > 1.5
- ALT or AST ≥ 5 times the ULN

In addition, for these patients, possible etiologies for acute hepatic injury should be excluded. The following laboratory tests should be performed: anti-hepatitis A IgM, hepatitis B surface antigen, anti-hepatitis B core IgM, hepatitis C antibody, hepatitis C quantitative RNA by polymerase chain reaction (PCR), anti-hepatitis E IgM. An extra blood sample should be collected and sent to the central laboratory for further diagnostic testing at a later date if needed. The patient should be followed clinically, and further medical evaluation should be done per the judgment of the investigator and in conjunction with medical personnel at Allergan. In general, the chemistry panel should be repeated 1 to 2 times per week to follow the course of ALT/AST elevation. For procedural details on the medical evaluation of liver disease, please see the Study Reference Manual.

The investigator should contact the Allergan Medical Monitor to discuss all cases of confirmed ALT/AST elevation ≥ 3 times the ULN. All ALT/AST elevations should be followed until ALT and AST return to < 1.5 times the ULN and there is full clinical resolution.

Study drug should be discontinued if any of the following criteria are met:

- ALT or AST ≥ 3 times the ULN and the patient is symptomatic with the appearance of fatigue, nausea, vomiting, right upper quadrant pain or tenderness, fever, rash, or eosinophilia ($> 5\%$)
- ALT or AST ≥ 3 times the ULN and total bilirubin > 2 times the ULN or INR > 1.5

- ALT or AST \geq 5 times the ULN for more than 2 weeks
- ALT or AST \geq 8 times the ULN

The patient may be rechallenged with ubrogepant upon consultation with the Allergan Medical Monitor. If a patient is not rechallenged with IP, the patient must be discontinued from the study and complete the ET Visit 15 and Safety Follow-Up Visit 16. Patients should receive appropriate follow-up as per standard of care.

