6.2.2 Events of Clinical Interest

Selected nonserious and serious events are of clinical interest and will require immediate reporting, recording and follow-up. The following events will be closely monitored:

- Suicidal ideations with intent, with or without a plan, (ie, Type 4 or 5 on the C-SSRS) or any suicidal behaviors
- Elevated ALT or AST laboratory value that is ≥ 3 times the ULN
- Potential Hy's law cases: elevated ALT or AST laboratory value that is ≥ 3 times the ULN and an elevated total bilirubin laboratory value that is ≥ 2 times the ULN and, at the same time, an alkaline phosphatase laboratory value that is < 2 times the ULN.

Reporting requirements for ALT or AST elevations and potential Hy's law cases are outlined in Sections 9.5 and 9.6. Responses to the C-SSRS that meet the above criterion will be captured in the electronic tablet (eTablet) and monitored by Allergan. Events that are determined to be AEs or SAEs must be reported appropriately via the designated eCRF pages and forms.

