7.3.2.7 Potential Hy's Law

Potential Hy's Law criteria within a 24-hour window is defined by a postbaseline elevation of alanine aminotransferase (ALT) or aspartate aminotransferase (AST) ≥ 3 times the ULN, along with total bilirubin (TBL) ≥ 2 times the ULN and a nonelevated alkaline phosphatase (ALP) < 2 times the ULN, all based on blood draws collected within a 24-hour period.

Potential Hy's Law criteria without time window (evaluation of drug-induced serious hepatotoxicity [eDISH]) is defined by maximum of postbaseline elevation of ALT or AST ≥ 3 times the ULN, along with maximum of postbaseline elevation of TBL ≥ 2 times the ULN.

Patients who meet the potential Hy's Law criteria from randomization to Visit 16 will be summarized. Supportive tabular displays also will be provided.

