9.6 Potential Hy's Law Cases

Sites must report every patient who meets the following potential Hy's law criteria if this occurs within the time the patient signs the ICF until 30 days after the last dose of ubrogepant:

- ALT or AST \geq 3 times the ULN, AND
- Total bilirubin \geq 2 times the ULN, AND
- Alkaline phosphatase $<$ 2 times the ULN

A laboratory alert for potential Hy's laws cases will be in place, and the investigators and Allergan will be notified immediately when the above criteria have been met. Any potential Hy's law case should be considered an SAE and also reported as an AE of Special Interest.

Both the SAE and AE of Interest Forms must be completed as soon as possible (within 24 hours of learning of the potential Hy's law) and faxed to the SAE/Pregnancy fax number [REDACTED]. The eCRF pages associated with potential Hy's law cases should be completed within 7 calendar days. Every effort to determine the cause of the liver abnormalities must be made, and close monitoring should be initiated in conjunction with the Allergan Medical Monitor and in accordance with the FDA "Guidance for Industry: Drug Induced Liver Injury - Pre-Marketing Clinical Evaluation," dated July 2009 ([FDA Guidance UCM174090, 2009](#)). For specific instructions, please refer to the Study Reference Manual.

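### Section 9.5 triggers its stop rule and hepatitis panel only above 2 × ULN bilirubin, while potential Hy's law includes exactly 2 × ULN, so one narrow boundary case is an SAE with no 9.5 stop or panel criterion

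*Protocol*

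**What the plan says.** Protocol 6.2.2 lists potential Hy's law among the events of clinical interest and requires "an elevated total bilirubin laboratory value that is ≥ 2 times the ULN", together with ALT or AST at or above 3 × ULN and ALP below 2 × ULN. Section 7.3.2.7 has the same limit for analysis, "total bilirubin (TBL) ≥ 2 times the ULN". Section 9.6 repeats the inclusive bilirubin limit for site reporting and adds that any potential Hy's law "case should be considered an SAE and also reported as an AE of Special Interest".

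Section 9.5 governs what happens after a confirmed ALT or AST elevation of at least 3 × ULN. It has three lists, and within each one bullet is enough.

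- The first follow-up list covers ALT/AST from 3 to 5 × ULN. Its first bullet is "≤ 5 times the ULN and who are asymptomatic with regard to possible liver disease", with no bilirubin or INR condition. Its second bullet needs "total bilirubin < 2 times the ULN and INR < 1.5", with no symptom condition.
- The second follow-up list adds hepatitis serology and PCR. It is met by symptoms, by "total bilirubin > 2 times the ULN or INR > 1.5", or by ALT/AST of 5 × ULN or more.
- The stop list is met by symptoms, by the same bilirubin/INR condition, by ALT/AST of 5 × ULN or more for over 2 weeks, or by ALT/AST of 8 × ULN or more.

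Section 9.6 gives no instruction on study drug and does not refer to 9.5. The liver-related withdrawal rule in 8.9 refers only to 9.5.

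**The concern.** The bilirubin limit is inclusive where the protocol defines the most serious liver signal and strict where it decides on the hepatitis panel and on stopping study drug. One would expect every potential Hy's law case to be placed somewhere in the stop rule. With different inequalities, a case sitting on the boundary is not.

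This matters more here than in most trials. Safety is the primary outcome, transaminase elevations go to an adjudication committee, and the background section reports that two earlier CGRP antagonists were abandoned after ALT increases. A liver decision threshold should classify the same result in one way throughout the protocol.

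**Working it through.** There is no sample size, power or error rate to recompute. The check is to write the rules as logical conditions and see which patients fall between them. Values are multiples of ULN, except INR.

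**Rules, from 9.5 and 9.6**

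- Potential Hy's law: ALT/AST ≥ 3, bilirubin ≥ 2 and ALP < 2.
- First list: ALT/AST 3 to 5, and either asymptomatic or (bilirubin < 2 and INR < 1.5).
- Second list: ALT/AST ≥ 3 with symptoms; or ALT/AST ≥ 3 with (bilirubin > 2 or INR > 1.5); or ALT/AST ≥ 5.
- Stop: ALT/AST ≥ 3 with symptoms; or ALT/AST ≥ 3 with (bilirubin > 2 or INR > 1.5); or ALT/AST ≥ 5 for more than 2 weeks; or ALT/AST ≥ 8.

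**Above the boundary.** If bilirubin exceeds 2, any potential Hy's law case has ALT/AST ≥ 3 and bilirubin > 2, which is itself a second-list and a stop criterion. There is no gap.

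**At bilirubin exactly 2.0 with ALP < 2.** Every row below is a potential Hy's law case.

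| ALT/AST | Symptoms | INR | Second list (hepatitis panel) | Stop |
|---|---|---|---|---|
| 3 to < 5 | no | ≤ 1.5 | not met | not met |
| 5 to < 8 | no | ≤ 1.5 | met | only after more than 2 weeks at ≥ 5 |
| ≥ 8 | no | ≤ 1.5 | met | met |
| ≥ 3 | yes | any | met | met |
| ≥ 3 | any | > 1.5 | met | met |

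Only the first row is the gap. That patient enters the first list through its asymptomatic bullet. The other bullet fails because 2.0 is not below 2.

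**Grid check.** The rules were evaluated at ALT/AST 3, 4, 5, 6, 8 and 9; INR 1, 1.5 and 1.6; symptoms yes or no; and duration 1 or 3 weeks. With bilirubin 2.0 that gives 6 × 3 × 2 × 2 = 72 combinations.

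- 12 met no stop criterion. Of these, 8 also met no second-list criterion: ALT/AST 3 or 4, INR 1 or 1.5, either duration, asymptomatic (2 × 2 × 2 = 8).
- The other 4 had ALT/AST 5 or 6 at 1 week (2 × 2 = 4) and met the second list.
- The results were the same whichever way the unbracketed *and/or* in the bilirubin/INR bullet is read.
- With one common inequality in 9.5 and 9.6, the number of gap combinations is 0.

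**Overlap of the two follow-up lists.** Adding bilirubin 1, 1.99, 2.01 and 3 and dropping duration gives 6 × 5 × 3 × 2 = 180 combinations. Of these, 39 meet both lists and none meets neither. Those in both include ALT/AST of exactly 5, asymptomatic 3 to 5 with bilirubin > 2 or INR > 1.5, and symptomatic 3 to 5 with bilirubin < 2 and INR < 1.5. Aligning the bilirubin limit would not remove this overlap. These counts show where the rules meet; they are not patient frequencies.

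**Analysis side.** The SAP uses bilirubin ≥ 2 × ULN for potential Hy's law in Table 5-22 and Table 6-13, in agreement with 6.2.2, 7.3.2.7 and 9.6. The readable SAP plans no count of patients meeting the 9.5 stop criteria.

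**The case against.** The strongest reply is that this is a one-symbol mismatch about a patient who is already looked after. Section 9.6 sets off an immediate laboratory alert and requires the site to seek the cause and monitor closely with the sponsor's Medical Monitor. Section 9.5 requires repeat testing with INR and an acetaminophen screen, chemistry once or twice a week, and contact with the Medical Monitor for every confirmed elevation. Section 8.9 allows the investigator to withdraw a patient judged to be at significant risk. Both 9.5 and 9.6 defer detail to a Study Reference Manual that is not among the documents.

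All of that stands, and it rules out reading the gap as a patient left without a work-up. What remains untriggered is specific: the hepatitis panel named in 9.5 and the stop criterion.

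A reader might also infer that the overlapping lists cause the gap, or give sites conflicting orders. They do neither. The gap comes from the inequality alone. The second list's hepatitis tests are worded as additional, its other actions largely repeat those of the first list, and nothing in the first list exempts a patient from the second. The stop list stands apart from both. The overlap is untidy but does not change discontinuations.

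Two further inferences fail. INR rounding does not widen the gap between 9.5 and 9.6, because potential Hy's law has no INR criterion. Nor is a difference between Hy's law counts and stop-rule counts evidence of error: the stop list includes symptoms, INR, duration and ALT/AST level and has no ALP condition, so the counts could differ even with identical bilirubin limits.

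**Conclusion.** The inconsistency is real and narrow. Section 9.5 uses a strict bilirubin limit and 6.2.2, 7.3.2.7 and 9.6 an inclusive one. As a result, a potential Hy's law SAE meets no 9.5 stop or hepatitis-panel criterion when bilirubin is exactly 2.0 × ULN, ALP is below 2 × ULN, ALT/AST is at least 3 and below 5 × ULN, INR is at most 1.5 and there are no symptoms. It would be wrong to say that potential Hy's law cases in general escape the stop rule: every case with bilirubin above 2 × ULN meets it.

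Very few patients should be affected. The documents give no rate of ALT/AST elevation. Assuming 0.5% to 2% of the 800 patients planned for the two ubrogepant arms reach 3 × ULN, 4 to 16 patients would enter 9.5 at all (0.005 × 800 = 4; 0.02 × 800 = 16), and the gap is a small part of that. No planned analysis changes. The point is worth correcting because it is a safety decision threshold that the protocol states in two ways. The conclusion rests on the protocol text alone; the Study Reference Manual may address the case, but the protocol should be consistent without it.

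**What to change.** Reconcile the bilirubin boundary in the second follow-up list and the stop list of 9.5 with 6.2.2, 7.3.2.7 and 9.6, and add a sentence to 9.5 stating how a case that meets 9.6 is handled. Which boundary and which action apply is for the clinical team to decide; either common inequality closes the gap. For clarity, also state how the two 9.5 follow-up lists relate when a patient meets both.

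The cost is wording in a protocol amendment or a letter to sites. No visits, samples, data fields or analyses are added. If the clinical team changed the Hy's law limit rather than the 9.5 limit, SAP Tables 5-22 and 6-13 would need the matching edit.

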9.6 Potential Hy's Law Cases

Sites must report every patient who meets the following potential Hy's law criteria if this occurs within the time the patient signs the ICF until 30 days after the last dose of ubrogepant:

- ALT or AST \geq 3 times the ULN, AND
- Total bilirubin \geq 2 times the ULN, AND
- Alkaline phosphatase $<$ 2 times the ULN

A laboratory alert for potential Hy's laws cases will be in place, and the investigators and Allergan will be notified immediately when the above criteria have been met. Any potential Hy's law case should be considered an SAE and also reported as an AE of Special Interest.

Both the SAE and AE of Interest Forms must be completed as soon as possible (within 24 hours of learning of the potential Hy's law) and faxed to the SAE/Pregnancy fax number [REDACTED]. The eCRF pages associated with potential Hy's law cases should be completed within 7 calendar days. Every effort to determine the cause of the liver abnormalities must be made, and close monitoring should be initiated in conjunction with the Allergan Medical Monitor and in accordance with the FDA "Guidance for Industry: Drug Induced Liver Injury - Pre-Marketing Clinical Evaluation," dated July 2009 ([FDA Guidance UCM174090, 2009](#)). For specific instructions, please refer to the Study Reference Manual.

9.7 Procedures for Unmasking of Investigational Product

When necessary for the safety and proper treatment of the patient, the investigator can unmask the patient's treatment assignment to determine which treatment has been assigned and institute appropriate follow-up care. When possible, the Allergan Medical Monitor should be notified prior to unmasking ubrogepant. The investigator should inform the Allergan Medical Monitor of the unmasking if there is no notification prior to the unmasking.

The treatment assignment for the patient can be determined by designated site personnel logging into the IWRS via password protected access. The reason for breaking the code must be recorded in the patient's source documents.

10. Administrative Items

This protocol is to be conducted in accordance with the applicable Good Clinical Practice (GCP) regulations and guidelines, eg, the International Conference on Harmonisation (ICH) Guideline on GCP.

10.1 Protection of Human Patients

10.1.1 Compliance with Informed Consent Regulations (US 21 CFR Part 50) and Relevant Country Regulations

Written informed consent is to be obtained from each patient prior to any study-related activities or procedures in the study, and/or from the patient's legally authorized representative.

10.1.2 Compliance with IRB or IEC Regulations

This study is to be conducted in accordance with IRB regulations (US 21 CFR Part 56.103) or applicable IEC regulations. The investigator must obtain approval from a properly constituted IRB/IEC prior to initiating the study and re-approval or review at least annually. Allergan is to be notified immediately if the responsible IRB/IEC has been disqualified or if proceedings leading to disqualification have begun. Copies of all IRB/IEC correspondence with the investigator should be provided to Allergan.

